Association between vitamin D and the risk of uterine fibroids

2018.3.16

Study objectives The primary objective of this part is to assess the efficacy of supplementation with vitamin D on decreasing the risk of incident uterine fibroids in one year and two years. The secondary objective of this study is to evaluate the safety of supplementation with vitamin D in subjects.

Trial design This is an open-label, randomised controlled trial. After signing of informed consent, hypovitaminosis D patients ($12 \text{ ng/ml} \le \text{serum } 25\text{-hydroxyvitamin}$ D₃ < 20 ng/ml) without uterine fibroids will be randomly assigned in a 1:1 ratio to intervention group or control group. Intervention group will receive an oral dose of 1600IU/day vitamin D₃ for up to 2 years. Control group will receive 2 years follow-up. Gynecologic ultrasound examinations will be performed every six months. The mount, location and size of the uterine fibroids will be documented. The safety of subjects will be evaluated, including blood routine examination, electrolyte, hepatic and renal function, liver and urinary system ultrasound, and serum 25-hydroxyvitamin D₃. Vitamin D receptor genotype of all patients will be tested. Vitamin D₃ Drops (soft capsules) are purchased from Sinopharm star shark pharmaceutical (xiamen) co., LTD and can be preserved for 2 years. An overview of the study design is shown in Figure 1 and in Table 1.

[figure not shown]

Figure 1: flow diagram.

Table 1:time of date collection									
Follow-up	1	2	3	4	5	6	7	8	9
Months	0	3	6	9	12	15	18	21	24
The form of follow-up	Out-patient								
Informed consent	X								
Medical history	X								
Physical examination	X								
Serum 25-hydroxyvitamin D ₃	X	X	X	X	X	X	X	X	X
Urine pregnancy test	X	X	X	X	X	X	X	X	X

Gynecologic ultrasound	X		X		X		X		X
Hepatic and renal function	X		X		X		X		X
Electrolyte	X		X		X		X		X
Blood routine examination	X		X		X		X		X
Liver and urinary System ultrasound	X				X				X
Side-effect assessment		X	X	X	X	X	X	X	X
Changes in menstruation		X	X	X	X	X	X	X	X
Adverse event assessment		X	X	X	X	X	X	X	X
Vitamin D receptor genotype	X								

Sample size The planned sample size was based on data from a previous study, in which the uterine fibroids incidence was 1.278% per year in Asia and 3.745% per year in African-American women. Women over the age of 40 years were more likely to have uterine fibroids. A study also revealed that African-American females had lower level of serum 25-hydroxyvitamin D_3 as compared to Caucasian females. Vitamin D deficiency was shown to increase the risk of uterine fibroids in vitro, in vivo animal models and in clinical trials. We assumed an one-tailed α error of 0.05 and a power (1- β) of 0.8. If the rates were 3.745% for the control group and 1.278% for the intervention group, we propose to enroll 1160 participants (580 randomized to each arm) and allow for a dropout rate of 10% for an effective sample size of 1054.

Inclusion criteria

- 1. Volunteer to participate in the study with informed consent;
- 2. Females aged 35-50 who are confirmed with a normal, fibroid-free uterine structure, by means of transvaginal or abdominal ultrasonography;
- 3. Serum25-hydroxyvitamin $D_3 < 20 \text{ ng/ml}$, $\geq 12 \text{ng/ml}$.

Exclusion criteria

- 1.Use of sexual hormone, mifepristone, gonadotropin-releasing hormone agonist (GnRHa), or other medication which is likely to interfere with uterine fibroids within 3 months;
- 2. Pregnancy, lactation, postmenopause, or planned pregnancy within two years;
- 3. Allergic to vitamin D₃;
- 4. Suspected or identified as other tumors of genital tract;
- 5. History of hysterectomy or myomectomy;
- 6. History of osteoporosis or vitamin D deficiency taking vitamin D supplements within previous one month;
- 7. History of hyperparathyroidism, infectious diseases (tuberculosis, AIDS), autoimmune diseases, or digestive system diseases (malabsorption, crohn disease and dysentery);
- 8. Alanine aminotransferase (ALT) or aspartate transaminase (AST) more than 3 times of the normal upper limit, total bilirubin (TBIL) more than 2 times of the normal upper limit;
- 9. Creatinine levels $\geq 1.4 \text{ mg/dL}$ (123µmol/L) or creatinine clearance $\leq 50 \text{ ml/min}$;

- 10. History of malignant tumors;
- 11. Simultaneous participation in another clinical study with investigational medicinal product(s) or researcher thinks the subjects are not suitable for this trial.

Outcomes measures

The primary outcome is first diagnosis of uterine fibroids in different groups.

The secondary outcomes include hypercalcemia, abnormal liver and renal function, and urinary calculus in different groups.

Withdrawal Subjects must be withdrawn from the study when one of the following criteria occurs:

- 1. At their own request. At any time during the study and without giving reasons, a subject may decline to participate further. The subject will not suffer any disadvantages as a result;
- 2. In the investigator's opinion, continuation of the study treatment would be harmful to the subject's health;
- 3. Obvious non-compliance;
- 4. Lost to follow-up;
- 5. Pregnancy;
- 6. Other medical or surgical treatments of uterine fibroids.
- 7. Receive other medical treatments which may affect the level of serum 25-hydroxyvitamin D₃ or other surgical treatments.
- 8. The level of serum calcium > 3.5 mmol/L or serum 25-hydroxyvitamin $D_3 > 100$ ng/mL.

Safety assessments Safety will be assessed by renal and liver function test, electrolyte, routine blood test, and serum 25-hydroxyvitamin D₃. Urine pregnancy test and serum 25-hydroxyvitamin D₃ level will be detected every three months. Other indicators are detected during the period of screening and after the treatment of every six months. Liver and urinary system ultrasound will be conducted after the treatment of 12 months and 24 months. The occurrence of any adverse events in trial participants will be recorded in the case report forms during each patient visit. We will withdraw patients who have severe adverse events, as it is unsafe for them to continue the trial. Meanwhile, we will give them relevant medical care and follow them up until the reaction has terminated.

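### The only efficacy outcome of this open-label trial depends on ultrasound reading, and the plan does not say that sonographers are kept unaware of the arm

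*Combined protocol and SAP*

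**What the plan says.** All references are to the combined protocol and SAP.

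- **Trial design.** "This is an open-label, randomised controlled trial". The comparator is unblinded follow-up: "Control group will receive 2 years follow-up". No placebo is described.
- **Trial design and Table 1.** "Gynecologic ultrasound examinations will be performed every six months". Table 1 places these scans at months 0, 6, 12, 18 and 24 on one schedule that does not differ by arm. It lists physical examination at month 0 only. For each fibroid found, the number, position and size are to be recorded. Serum 25-hydroxyvitamin D is measured every three months.
- **Outcomes measures.** "The primary outcome is first diagnosis of uterine fibroids in different groups". The others concern safety only: "The secondary outcomes include hypercalcemia, abnormal liver and renal function, and urinary calculus in different groups".
- **Sample size.** "We assumed an one-tailed α error of 0.05", with power 0.8. The planning assumption is "If the rates were 3.745% for the control group and 1.278% for the intervention group". Enrolment is 580 per arm, and the plan will "allow for a dropout rate of 10% for an effective sample size of 1054".

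No section of the available text mentions masking of sonographers or other outcome assessors, independent reading, adjudication, or a minimum size for a lesion to count as a fibroid.

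**The concern.** Open-label treatment does not by itself compromise an outcome. It does mean that whoever decides the outcome can learn the arm unless something prevents it. Here that decision is a yes/no reading of a scan. With no size threshold, a small or doubtful finding is left to the reader. A sonographer who knows the arm could, without intending to, call such findings more readily in untreated women, or less readily in women taking vitamin D. The opposite is equally possible.

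Events are few, so a handful of readings matters, and no second efficacy outcome is named against which the result could be checked. Error towards benefit could raise the chance of a false claim of efficacy. Error in the other direction could hide a real effect.

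**Working it through.** **Inputs from the plan (Sample size).** One-sided α = 0.05, so z = 1.645; planning rates 3.745% and 1.278%; 580 per arm; 10% dropout.

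**Number per arm.** 580 × 0.9 = 522. The plan's 1054 gives 527 per arm, and 527 × 1.1 = 580, so the plan inflated by multiplying. The two figures differ too little to matter here. I use 522.

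**The plan's own power.** For rates p1 (control) and p2 (intervention), with mean p̄:

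- S0 = √[2p̄(1−p̄)/n]
- S1 = √[(p1(1−p1) + p2(1−p2))/n]
- P(reject) = Φ[((p1−p2) − 1.645·S0)/S1]

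With 3.745%, 1.278% and n = 522, this gives 81.7%, against the stated 80%. The plan's figure is reproduced closely enough to use the same formula below.

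**Assumptions that are not in the plan.** No true effect; one of the plan's two rates taken as the common incidence, without compounding over two years; 10% or 20% of events misread in one arm only, towards benefit. The plan names no test, so I show a pooled z test and a one-sided Fisher test (exact enumeration).

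**What this means in women.** At 3.745%, 522 × 0.03745 = 19.5 events per arm, so 10% or 20% is about 2 or 4 women. At 1.278%, 522 × 0.01278 = 6.7 events, so 10% or 20% is about 0.7 or 1.3 women.

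**One case in full.** Common incidence 3.745%, controls over-called by 10%: p1 = 4.1195%, p2 = 3.745%, difference 0.003745, S0 = 0.01203, S1 = 0.01203. Then (0.003745 − 1.645 × 0.01203)/0.01203 = −1.33, and Φ(−1.33) is about 0.091.

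**False-positive rates, 522 per arm, one-sided 0.05:**

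| Common incidence | Misreading in one arm | Pooled z | Fisher |
|---|---|---|---|
| 3.745% | none | 5.0% | 3.5% |
| 3.745% | 10%, controls over-called | 9.1% | 6.7% |
| 3.745% | 10%, intervention under-called | 9.4% | 6.8% |
| 3.745% | 20%, controls over-called | 15.0% | 11.6% |
| 3.745% | 20%, intervention under-called | 16.5% | 12.4% |
| 1.278% | none | 5.0% | 2.7% |
| 1.278% | 10%, controls over-called | 7.1% | 4.1% |
| 1.278% | 10%, intervention under-called | 7.3% | 4.0% |
| 1.278% | 20%, controls over-called | 9.8% | 6.0% |
| 1.278% | 20%, intervention under-called | 10.4% | 5.9% |

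Exact enumeration of the pooled z test agrees with the normal approximation within 0.3 percentage point.

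**The other direction.** Suppose the planned effect is real and 10% of control events are missed. Then p1 = 3.3705%, p2 = 1.278%, difference 0.020925, S0 = 0.009326, S1 = 0.009304. So (0.020925 − 1.645 × 0.009326)/0.009304 = 0.60, and power falls from 81.7% to about 73%. With 20% missed, p1 = 2.996%, difference 0.01718, S0 = 0.008951, S1 = 0.008936, the argument is 0.27, and power is about 61%.

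**The case against.** The strongest reply is that this argues from silence in a very short document. Open-label describes the treatment, not the reading of scans. The text does not cover who scans or what the request forms carry, and Figure 1 is not available. A reader might infer that sonographers know the arm, or that the result will be biased. The documents support neither. They show only that no safeguard is stated.

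The design also gives real protection. Women are randomised, all must be fibroid-free on ultrasound at entry, and both arms share one scan schedule, so the frequency of looking does not differ by arm. Recording number, position and size leaves something that can be checked. This limits the problem, but it does not stop a doubtful image being called differently when the arm is known.

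The outcome definition does not itself mention ultrasound. That the diagnosis rests on it is inferred from Trial design and Table 1, which schedule no other method of detection after baseline.

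Finally, the misreading rates come from no document, and the direction of any error is unknown. A reader might conclude that misreading towards benefit must push the error rate above 5%. It need not: with Fisher's test at 1.278% and 10% misreading it stays at about 4%. These objections limit how strongly the point can be put. They do not supply the missing safeguard.

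**Conclusion.** The point stands as a gap in a stated safeguard, not as a demonstrated bias. The only efficacy conclusion depends on scan readings with no size threshold, in an open-label trial, and the available text does nothing to keep the readers unaware of allocation.

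The possible size is material but unknown. Under the assumptions listed, misreading 10% or 20% of events in one arm towards benefit could give a false-positive rate anywhere from about 4% (Fisher, 1.278%, 10% misread) to about 16% (pooled z, 3.745%, 20% misread). These are illustrations over a range, not estimates. The change should be made because it is cheap and protects the single efficacy result. Confidence is medium, since the safeguard may already exist in practice without being written down.

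**What to change.** Add a short paragraph to Trial design or Outcomes measures stating that:

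- the sonographers already performing the study scans are not told the allocation;
- scan request forms omit the arm and the follow-up 25-hydroxyvitamin D results, which could reveal it;
- women are asked not to tell the sonographer which arm they are in.

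If this is already the practice, the paragraph only records it. The cost is one paragraph, a change to the request form and a small logistic burden at each scan visit. No extra reader, scan or procedure is needed, and the sample size does not change. Masking will be imperfect if women disclose their arm, so the safeguard reduces the risk by an amount that cannot be stated in advance.

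### The plan names age over 40 as a risk factor and enrols on both sides of it, but specifies neither age-stratified randomisation nor an age-adjusted primary comparison

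*Combined protocol and SAP*

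**What the plan says.** The Sample size section gives age as a risk factor: "Women over the age of 40 years were more likely to have uterine fibroids". It gives no size for the age effect and does not say whether the remark concerns existing or newly arising fibroids.

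Inclusion criterion 2 admits "Females aged 35-50 who are confirmed with a normal, fibroid-free uterine structure", so the trial recruits on both sides of 40.

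On allocation, the Trial design section says that women "will be randomly assigned in a 1:1 ratio to intervention group or control group". No stratification factor, block scheme or minimisation is named. Figure 1 is not available and could not be checked.

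On the comparison, the Outcomes measures section says: "The primary outcome is first diagnosis of uterine fibroids in different groups". No test, model or covariate appears anywhere in the document.

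**The concern.** A plan that singles out a prognostic factor and enrols across its threshold would be expected to use it in the allocation, in the analysis, or in both. Age is an eligibility criterion, so it is on record for every woman before randomisation.

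Two things are at stake. First, if the arms differ in age by chance, the difference passes straight into an unadjusted risk ratio. Second, nothing is said about adjustment in an open-label trial tested one-sided at 0.05. If the arms turn out unequal, a decision to adjust and a decision not to adjust would both be made after the data are seen, and both would be open to challenge.

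**Working it through.** **Inputs from the plan.** Annual rates are 3.745% (control) and 1.278% (intervention), a risk ratio of 1.278/3.745 = 0.34. Alpha is 0.05 one-sided and power is 0.80. Enrolment is 1160 and the effective sample size is 1054, or 527 per arm. The horizons are one and two years.

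**The plan's own figure.** 1054 × 1.10 = 1159.4, which rounds up to the 1160 enrolled. No formula is named for 1054. At 527 per arm, power is 0.783 by a one-sided Fisher exact test and 0.8205 by a pooled z test without continuity correction, so the figure is in the right region. It does not depend on age and needs no change for this point.

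**Assumptions not in the plan.** The share of women over 40 is f = 0.5. The relative risk for over 40 against 40 or under is R = 1.5, 2 or 3. The two-year control risk is 1 − (1 − 0.03745)² = 0.0735, which takes the annual rate as constant.

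**Step 1: size of a chance imbalance.** Without stratification, the standard deviation of the between-arm difference in the share over 40 is √(2 × 0.5 × 0.5 / 527) = 0.0308. The 95% limit is D = 1.96 × 0.0308 = 0.060, or 6.0 percentage points.

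**Step 2: shift in the risk ratio at that limit, with no treatment effect.** The ratio of control to intervention risk is [1 + (f + D/2)(R − 1)] / [1 + (f − D/2)(R − 1)].

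**Step 3: conditional one-sided error of an unadjusted test when the excess of older women is in the control arm.** With control risk p:
- risk in the younger band: r₀ = p / [1 + f(R − 1)]
- shift in the risk difference: D × r₀ × (R − 1)
- standard error: √(2p(1 − p)/527), which is 0.0117 at one year and 0.0161 at two
- conditional error: 1 − Φ(1.645 − shift/SE)

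| R | Risk-ratio shift | Shift/SE, 1 year | Error, 1 year | Shift/SE, 2 years | Error, 2 years |
|---|---|---|---|---|---|
| 1.5 | 1.024 | 0.077 | 0.0585 | 0.110 | 0.0624 |
| 2 | 1.041 | 0.129 | 0.0647 | 0.184 | 0.0720 |
| 3 | 1.062 | 0.193 | 0.0733 | 0.276 | 0.0855 |

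Varying the share over 40 from 40% to 67%, with R from 1.5 to 3 and both horizons, widens the conditional error only to about 5.7% to 8.9%.

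**Step 4: behaviour averaged over all randomisations.** This was simulated at 527 per arm with the plan's one-year rates, 67% over 40 and R from 1.5 to 3.
- Unstratified and unadjusted: type I error 0.049 to 0.051, power 0.840 to 0.841.
- Unstratified with a Mantel-Haenszel test: power 0.839 to 0.841, so adjusting alone costs at most about 0.1 points.
- Stratified with a Mantel-Haenszel test: power 0.841 to 0.844, a gain of at most about 0.3 points.

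**The case against.** The strongest reply is that the harm is slight. Averaged over randomisations, the unadjusted test already has its nominal error. An imbalance at or beyond the limit, against controls, arises in only about 2.5% of randomisations. Even there the shift is at most about 0.28 standard errors, beside a planned risk ratio of 0.34. All of that stands and fixes the weight of the point.

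The size also rests on assumed inputs. The plan gives neither an age distribution nor an age effect, and its remark on women over 40 may describe how many have fibroids rather than how many develop them. This stands too, and is why the age effect is shown from 1.5 upward.

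A reader might make three stronger inferences that the documents do not support:
- **That the plan chose simple randomisation and a crude comparison.** It is silent on both. A 1:1 ratio is compatible with blocks, strata or minimisation, and the outcome sentence defines an outcome, not an analysis. The wider gap is that no randomisation method or primary analysis is stated; age is one part of it.
- **That few expected events make the matter worse.** At the plan's rates, 527 per arm gives about 20 and 7 events at one year and 39 and 13 at two. But imbalance depends on the number randomised, and fewer events make the shift smaller relative to its standard error (0.129 at one year against 0.184 at two, for R = 2).
- **That baseline 25-hydroxyvitamin D₃ should be adjusted for as well.** Eligibility confines it to 12 to below 20 ng/ml. The plan shows no risk gradient within that range, and no benefit has been calculated.

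**Conclusion.** The point holds as a minor, inexpensive improvement. The plan names age over 40 as a risk factor, recruits on both sides of it, and specifies no use of it in allocation or analysis. This does not invalidate the planned test or the sample size.

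What is gained is conditional protection. With half the women over 40 and an age relative risk of 1.5 to 3, both assumed, a 6-point imbalance shifts the risk ratio by about 2% to 6% and takes the one-sided error from 5% to about 6% to 9% when controls are the older arm. The second gain, which does not depend on those assumptions, is that the choice to adjust is no longer left until after the results are seen.

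**What to change.** Stratify the randomisation by age, 40 or under against over 40, if that is still possible. This cut matches the plan's own boundary; a split at below 40 against 40 and above would put women aged exactly 40 in the higher-risk band.

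Whether or not stratification is possible, name one primary comparison before outcome data are examined: a Mantel-Haenszel test and risk ratio across the two age bands. Report the unadjusted result as support. Naming a single method matters, because a list of alternatives would leave the post-hoc choice in place.

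The cost is one line in the randomisation set-up and one sentence in the analysis text. No patients, visits or measurements are added, the sample size is unchanged, and no material power is lost.

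### The trial is sized at a one-tailed 5% level, and no level, test or primary time point is set for the analysis; a two-sided 5% test at 24 months would fit the planned sample on the plan's own rates.

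*Combined protocol and SAP*

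**What the plan says.** The Sample size section gives the only error rate in the documents: "We assumed an one-tailed α error of 0.05", with "a power (1- β) of 0.8". The sizing condition is "If the rates were 3.745% for the control group and 1.278% for the intervention group". These are annual figures from two different populations: "the uterine fibroids incidence was 1.278% per year in Asia and 3.745% per year in African-American women". From them, "we propose to enroll 1160 participants (580 randomized to each arm"), with a 10% dropout allowance and a stated effective size of 1054.

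Study objectives puts the primary aim as "decreasing the risk of incident uterine fibroids in one year and two years", with neither time point ranked first. Trial design says "This is an open-label, randomised controlled trial", with women "randomly assigned in a 1:1 ratio to intervention group or control group", two years of follow-up and six-monthly gynecologic ultrasound. Table 1 schedules that ultrasound at 0, 6, 12, 18 and 24 months. Outcomes measures defines the primary outcome as the first fibroid diagnosis, without a time point.

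There is no analysis section. No test, sidedness, significance level, confidence level or rule for handling two time points is given.

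**The concern.** A one-tailed 5% level allows a 5% chance of declaring benefit when there is none. The usual two-sided 5% test allows 2.5% in that direction. If the final analysis uses the sizing level, a one-tailed p between 0.025 and 0.05 would count as success although the two-sided 95% confidence interval would include no effect. Many readers would dispute such a result.

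Two features make this more than a matter of taste. First, the 80% power holds only at the lenient level; at a two-sided 5% level the same sample and one-year rates fall well short. Second, because the analysis level and the primary time point are both unstated, either could be settled after the results are seen. With two unranked time points, the chance of a false claim could exceed 5%.

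**Working it through.** **Inputs.** From Sample size: annual rates p1 = 0.03745 (control) and p2 = 0.01278 (intervention), 580 enrolled per arm, 10% dropout. Evaluable per arm is 580 × 0.90 = 522. The plan's 1054 is 527 per arm; it fits 1054 × 1.1 = 1159.4, whereas 1160 less 10% is 1044. I use 522; using 527 moves the three headline powers by at most 0.4 points.

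**Formula.** Pooled-variance comparison of two proportions, with mean rate p̄ = (p1 + p2)/2:

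- SE0 = √[2p̄(1 − p̄)/n]
- SE1 = √{[p1(1 − p1) + p2(1 − p2)]/n}
- power = Φ[(p1 − p2 − z·SE0)/SE1], with z = 1.645 for one-sided 5% and 1.960 for two-sided 5%

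**Step 1: the plan's own figure.** For 80% power at one-sided 5% on one-year rates, the formula needs 497 per arm (994 evaluable, 5.7% below 1054). Fisher's exact test needs 549 per arm (1098, 4% above). Power at the planned size is 81.7% (pooled, 522), 82.0% (pooled, 527) or 78.3% (Fisher, 527). So 80% is bracketed, although 1054 is not reproduced exactly. Two-sided sizing gives 631 per arm (1262), which does not fit. The size therefore does rest on the one-tailed level and one-year rates.

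**Step 2: one year, 522 per arm.** p1 − p2 = 0.02467, SE0 = 0.009686, SE1 = 0.009655.

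- One-sided 5%: (0.02467 − 1.645 × 0.009686)/0.009655 = 0.905, power 81.7% (Fisher 77.9%)
- Two-sided 5%: (0.02467 − 1.960 × 0.009686)/0.009655 = 0.589, power 72.2% (Fisher 67.6%)

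Reaching 80% two-sided at one year needs 1262 evaluable, or 1262/0.90 ≈ 1403 enrolled. That is about 240 more than planned.

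**Step 3: 24 months, 522 per arm.** Assuming the same annual risk in both years, cumulative risk is 1 − (1 − p)²: 7.350% and 2.540%. The difference is 0.04810, SE0 = 0.01342, SE1 = 0.01334. Two-sided 5%: (0.04810 − 1.960 × 0.01342)/0.01334 = 1.63, power 94.9% (Fisher 94.5%). For 80% power, 318 per arm would do.

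**Step 4: sensitivity to the rates** (same formula, 522 per arm):

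| Annual rates, control vs intervention | 12 months, one-sided 5% | 24 months, two-sided 5% | 24 months, one-sided 5% |
|---|---|---|---|
| 3.745% vs 1.278% (plan) | 81.7% | 94.9% | 97.5% |
| 3.745% vs 1.873% (halved) | 57.4% | 73.1% | 82.4% |
| 2.5% control, plan's ratio 0.341 | 66.6% | 83.3% | 90.0% |
| 2% control, same ratio | 58.2% | 74.3% | 83.4% |
| 1.278% control, same ratio | 43.3% | 54.9% | 67.0% |

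In every row the 24-month two-sided test has more power than the current 12-month one-sided basis. The last two columns show what the stricter threshold itself costs at 24 months: about 3 to 12 points. Heavier loss matters less: with the plan's rates and 20% loss (464 per arm), 24-month two-sided power is 92.3%.

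**Step 5: claiming at either time point.** Suppose both comparisons are tested one-sided at 5%, unadjusted, and either may support a claim. About half of the 24-month events fall in year one, so I take the correlation of the two statistics as √0.5 = 0.71. The bivariate normal then gives an 8.0% chance of at least one false claim. With correlations from 0.5 to 0.9 the range is 8.8% to 6.8%.

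**The case against.** The strongest reply is that a one-sided 5% level is a disclosed design choice. The objective is directional, and Sample size cites laboratory, animal and clinical evidence that deficiency raises fibroid risk. That supports a directional hypothesis. It does not explain why the level should be 5% rather than 2.5% in that direction, so the point stands. The open-label design, however, has no bearing on sidedness and is not part of the argument.

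Four stronger readings are tempting, and the documents do not support them:

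- *That the trial will be tested one-sided at 5%.* The level appears only as a sizing assumption. Its use in the analysis is an inference.
- *That harm could not be reported.* A one-sided sizing level does not stop the investigators from giving an estimate and interval in either direction.
- *That a two-sided test is free.* It needs no extra women only if 24 months becomes the single primary time point. This takes one year out of an objective that now names both.
- *That the trial simply has 95% power at 24 months.* That figure pairs an African-American rate for control with an Asian rate for intervention and holds both constant for two years.

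The 8% figure is also conditional: the documents state no either-time success rule. The unranked time points are a separate gap that a two-sided test alone would not close.

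**Conclusion.** The concern holds in a limited form. The sizing rests on a one-tailed 5% level, and nothing else fixes how the primary comparison will be judged. If the analysis follows the sizing, the false-benefit risk is twice the conventional 2.5%, and the stated power drops by about 10 points at one year under a two-sided 5% test (81.7% to 72.2%).

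A two-sided 5% test at 24 months halves the false-benefit risk relative to the sizing level and keeps more power than the present basis at every rate tried. How much power it has depends on the assumed rates: from 55% to 95% across the scenarios shown. The comparison assumes constant annual risk and 522 evaluable women per arm at 24 months. This is an inexpensive improvement worth making; it does not show that the design is unworkable.

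**What to change.** In Sample size, and in an analysis paragraph to be added:

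1. Name the cumulative incidence of a first fibroid at 24 months as the single primary comparison. State the test, at two-sided 5% (equivalently one-sided 2.5%), with a two-sided 95% confidence interval.
2. Make the one-year comparison secondary, and align Study objectives and Outcomes measures with this.
3. Keep 1160 and restate power as conditional: about 95% if the plan's annual rates hold for two years, and about 73% if 3.745% is only halved. With the plan's rate ratio, give 83%, 74% and 55% at annual control rates of 2.5%, 2% and 1.278%.
4. If one year is kept as primary, state its two-sided power as about 72%.

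The cost is wording, a stricter threshold, and the loss of the one-year comparison's equal standing in the primary objective. No patients or visits are added, since the 24-month ultrasound is already scheduled.

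### Effective sample size misstated: 1160 enrolled less 10% dropout leaves 1044, not 1054

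*Combined protocol and SAP*

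**What the plan says.** The whole calculation is in the Sample size section of the combined protocol and SAP.

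- Error rates: "We assumed an one-tailed α error of 0.05 and a power (1- β) of 0.8".
- Effect: "If the rates were 3.745% for the control group and 1.278% for the intervention group". The sentence introducing these rates gives both as annual incidences: "uterine fibroids incidence was 1.278% per year in Asia and 3.745% per year in African-American women".
- Enrolment: "we propose to enroll 1160 participants (580 randomized to each arm"), which agrees with the equal allocation under Trial design.
- Dropout: the plan will "allow for a dropout rate of 10% for an effective sample size of 1054".

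The section names neither the statistical test nor the sample-size formula, and it does not show how the dropout allowance was applied. Nothing elsewhere in the document gives another dropout rate or another effective size.

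**The concern.** A dropout rate is ordinarily a share of the women enrolled, and the sentence presents 1054 as what is left once that share has gone. Read that way, 1160, 10% and 1054 cannot all be right. Rounding per arm could shift a total by one or two, not by ten.

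Two things are at stake. First, a core design figure does not follow from the plan's own inputs, and any later account that repeats it repeats the error. Second, the effective size is a natural yardstick for retention: a trial that lost exactly the planned 10% would finish with 1044 women and seem to have missed its target by ten. The check also has to establish whether the missing ten women threaten the planned 80% power.

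**Working it through.** **Inputs** (Sample size section): 1160 enrolled, 580 per arm; dropout 10%; effective size 1054, that is 527 per arm; one-sided α 0.05; power 0.80; rates 3.745% (control) and 1.278% (intervention).

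**1. Reproducing the printed pair.** Multiplying by one plus the dropout rate:
- total: 1054 × 1.10 = 1159.4, rounded up to 1160;
- per arm: 527 × 1.10 = 579.7, rounded up to 580.

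This route gives the printed enrolment exactly.

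**2. Applying 10% as a share of those enrolled.**
- Remaining: 1160 × (1 − 0.10) = 1044; per arm 580 × 0.90 = 522.
- Difference from the stated figure: 1054 − 1044 = 10 women, 5 per arm; 10/1054 = 0.95%.
- Loss implied by the printed pair: 1 − 1054/1160 = 9.1%.
- Enrolment needed to keep 1054 after a 10% loss: 527/0.90 = 585.6, so 586 per arm, 1172 in total (12 more than planned).

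**3. Effect on one-year power.** Pooled normal approximation, no continuity correction:

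power = Φ{ [ d√n − z(0.95)·√(2p̄(1 − p̄)) ] / √(p₁(1 − p₁) + p₂(1 − p₂)) }

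with p₁ = 0.03745, p₂ = 0.01278, d = 0.02467, p̄ = 0.025115. The null term is 1.645 × 0.22129 = 0.36399 and the denominator is 0.22060.
- n = 527: (0.56634 − 0.36399)/0.22060 = 0.917, power 82.0%.
- n = 522: (0.56364 − 0.36399)/0.22060 = 0.905, power 81.7%.

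The loss is 0.3 percentage points. Solving the same formula for 80% power gives n = 496.4, so 497 per arm and 994 in total. On this test, 1160 enrolled would tolerate 1 − 994/1160 = 14.3% dropout before one-year power fell below 80%.

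**4. Sensitivity to the unnamed test.** One-year power, one-sided 0.05:

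| Test | 527 per arm | 522 per arm |
|---|---|---|
| Two proportions, uncorrected | 82.0% | 81.7% |
| Fisher's exact | 78.3% | 77.9% |
| Two proportions, continuity-corrected | 76.4% | 76.0% |

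For every test the change from 527 to 522 is 0.3 to 0.4 points. Where power is under 80%, it is under 80% at both sizes.

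**5. Two-year comparison.** The Study objectives look at both one and two years. If the annual rates are assumed constant, the two-year risks 1 − (1 − p)² are 7.35% and 2.54%. The formula in step 3 then gives 97.6% at 527 per arm and 97.5% at 522.

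**The case against.** The strongest reply is that the plan never says what the 10% is a percentage of. If it is a margin added to the required number, 527 × 1.1 rounds up to 580 and the printed figures agree. That probably explains how they arose, but it does not rescue the wording: the sentence calls the 10% a dropout rate and treats 1054 as the number left, and on that reading the answer is 1044.

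A second reply is that, if 1054 was the target, then 1160 is the wrong number and enrolment should rise to 1172. This cannot be settled from the document, because the origin of 1054 is not shown. On the stated rates with one-sided 0.05, the uncorrected formula needs 994 in total and the continuity-corrected one 1150; neither is 1054. If the sponsor can show that 1054 was a firm requirement, 1172 is the consistent enrolment. Without that, there is no evident reason to add women, since 1044 already exceeds the 994 needed by the uncorrected test.

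Third, the reassurance on power depends on a test the plan does not name. This stands. With Fisher's exact test or a continuity correction, one-year power misses 80%, but it does so at 1054 as well, so it is a separate matter from the dropout error.

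Finally, the discrepancy is small. That is accepted, and it limits the rating.

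**Conclusion.** The concern holds, as a minor error in a stated figure. With 1160 enrolled and 10% dropout the effective size is 1044 (522 per arm), 10 fewer than the plan states. This needs only the reading of dropout as a share of those enrolled; it does not depend on the test, the rates or the follow-up time.

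The power cost is about 0.3 points. That one-year power remains above 80% (81.7%) rests on the plan's assumed rates, one-sided 0.05 and an uncorrected two-proportion test. The two-year figure of 97.5% additionally assumes constant annual rates, which the document does not state. The dropout error alone gives no reason to change enrolment or design.

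**What to change.** Keep 1160 enrolled (580 per arm) and rewrite the last clause of the Sample size section to say that 10% dropout gives an effective sample size of 1044, 522 per arm. In the same place, name the test and give the power at 522 per arm: 81.7% at one year if it is the uncorrected two-proportion test, otherwise the figure for the test chosen.

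The cost is a one-sentence correction, with no extra women and no change to the design. Only if the sponsor documents 1054 as a required number would the alternative apply: enrol 1172 (586 per arm), 12 more women.
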